## 8.2 Responsibility for Analyses/In-House Blinding

**Note: As of Amendment 06, the study will be unblinded to the Sponsor, the investigational sites, and the participants.**

The statistical analysis of the data obtained from this study will be the responsibility of the Clinical Biostatistics department of the Sponsor.

This study will be conducted as a double-blinded study under in-house blinding procedures. The official, final database will not be unblinded until medical/scientific review has been performed, protocol deviations have been identified, and data have been declared final and complete.

The Sponsor will generate the randomized allocation schedule(s) for study treatment assignment for this protocol, and the randomization will be implemented in an IVRS/IWRS.

Planned interim analyses are described in Section 8.7 – Interim Analyses. Blinding to treatment assignment will be maintained at all investigational sites. Treatment-level results of the planned interim analyses will be provided by the external unblinded statistician to the DMC. Limited additional Sponsor personnel may be unblinded to the treatment level results of the interim analyses, if required, in order to act on the recommendations of the DMC (e.g., interaction with regulatory agencies). The extent to which individuals are unblinded with respect to results of interim analyses will be documented by the unblinded statistician.

The DMC will serve as the primary reviewer of the results of the interim analyses and will make recommendations for discontinuation of the study or modification to an EOC of the Sponsor. Depending on the recommendation of the DMC, the Sponsor may prepare a regulatory submission. If the DMC recommends modifications to the design of the protocol or discontinuation of the study, this EOC and limited additional Sponsor personnel may be unblinded to results at the treatment level in order to act on these recommendations. The DMC responsibilities, review schedules, and additional logistical details will be provided in the DMC Charter.

Prior to final study unblinding, the external unblinded statistician will not be involved in any discussions regarding modifications to the protocol, statistical methods, identification of protocol deviations, or data validation efforts after the interim analyses.

### **8.3 Hypotheses/Estimation**

Objectives and hypotheses of the study are stated in Section 3 – Objective(s) & Hypothesis(es).

### **8.4 Analysis Endpoints**

Efficacy and safety endpoints that will be evaluated for within- and/or between-treatment differences are listed below. Exploratory endpoints will be described in the sSAP.

#### **8.4.1 Efficacy Endpoints**

##### **Primary Endpoints**

###### **Overall Survival**

OS is defined as the time from randomization to death due to any cause. Subjects without documented death at the time of analysis will be censored at the date of last known contact.

###### **Progression-free Survival**

PFS is defined as the time from randomization to the first documented disease progression per RECIST 1.1 based on BICR or death due to any cause, whichever occurs first. See Section 8.6.1.2 – Progression-free Survival for the definition of censoring.

##### **Secondary Endpoints**

###### **Objective Response Rate**

ORR is defined as the proportion of subjects who have a CR or a PR. Responses are based on confirmed assessments by BICR per RECIST 1.1.

###### **Duration of Response**

For subjects who demonstrate CR or PR, DOR is defined as the time from first documented evidence of CR or PR until disease progression per RECIST 1.1 as assessed by BICR or death due to any cause, whichever occurs first.

###### **Change from baseline in global health status/quality of life**

This is defined as a change from baseline in the global health status/quality of life score from the EORTC QLQ-C30 (items 29 and 30).

### **Time to true deterioration in cough, pain in chest, and shortness of breath**

TTD is defined as the time to the first onset of a 10-point or greater score deterioration from baseline in any one of the 3 symptoms, confirmed by a second adjacent 10-point or greater score deterioration from baseline. Cough is based on EORTC QLQ-LC13 question 1, pain in chest is based on EORTC QLQ-LC13 question 10, and shortness of breath is based on EORTC QLQ-C30 question 8.

#### **8.4.2 Safety Endpoints**

Safety measurements are described in Section 4.2.3.3 – Safety Endpoints and Section 7 – Trial Procedures. Safety and tolerability will be assessed by clinical review of all relevant parameters including AEs, SAEs, fatal AEs, laboratory tests, and vital signs. Safety parameters to be analyzed include, but are not limited to, AEs, SAEs, fatal AEs, and laboratory changes.

#### **8.5 Analysis Populations**

##### **8.5.1 Efficacy Analysis Populations**

The ITT population will serve as the population for primary efficacy analysis. All randomized subjects will be included in this population. Subjects will be included in the treatment group to which they are randomized.

Details on the approach to handling missing data are provided in Section 8.6 – Statistical Methods.

##### **8.5.2 Safety Analysis Populations**

The All Subjects as Treated (ASaT) population will be used for the analysis of safety data in this study. The ASaT population consists of all randomized subjects who received at least 1 dose of study treatment. Subjects will be included in the treatment group corresponding to the study treatment they actually received for the analysis of safety data using the ASaT population. For most subjects, this will be the treatment group to which they are randomized. Subjects who take incorrect study treatment for the entire treatment period will be included in the treatment group corresponding to the study treatment actually received. Any subject who receives the incorrect study medication for 1 cycle, but receives the correct treatment for all other cycles, will be analyzed according to the correct treatment group and a narrative will be provided for any events that occur during the cycle for which the subject is incorrectly dosed.

At least 1 laboratory or vital sign measurement obtained after at least 1 dose of study treatment is required for inclusion in the analysis of each specific parameter. To assess change from baseline, a baseline measurement is also required. Details on the approach to handling missing data for safety analyses are provided in Section 8.6 – Statistical Methods.

##### **8.5.3 Patient-reported Outcomes Analysis Populations**

The PRO analyses are based on the PRO full analysis set (FAS) population, defined as subjects who have at least 1 PRO assessment available and have received at least 1 dose of study medication.

## **8.6 Statistical Methods**

### **8.6.1 Statistical Methods for Efficacy Analyses**

This section describes the statistical methods that address the primary and secondary objectives. Methods related to exploratory objectives will be described in the sSAP.

Efficacy results that will be deemed to be statistically significant after consideration of the Type I error control strategy are described in Section 8.8 – Multiplicity. Nominal p-values will be computed for other efficacy analyses, but should be interpreted with caution due to potential issues of multiplicity.

The stratification factors used for randomization (see Section 5.4 – Stratification) will be applied to all stratified analyses, in particular, the stratified log-rank test, stratified Cox model, and stratified Miettinen and Nurminen method [42]. In the event that there are small strata, for the purpose of analysis, strata will be combined to ensure sufficient number of participants, responses and events in each stratum. Details regarding the pooling strategy will be prespecified in the sSAP prior to the database lock for the first analysis when each applicable endpoint will be analyzed, and decisions regarding the pooling will be based on a blinded review of response and event counts by stratum.

#### **8.6.1.1 Overall Survival**

The nonparametric Kaplan-Meier method will be used to estimate the survival curve in each treatment group. The treatment difference in survival will be assessed by the stratified log-rank test. A stratified Cox proportional hazard model with Efron's method of tie handling will be used to assess the magnitude of the treatment difference (i.e., the hazard ratio). The hazard ratio and its 95% CI from the stratified Cox model with Efron's method of tie handling and with a single covariate for treatment will be reported. The stratification factors used for randomization (see Section 5.4– Stratification) will be applied to both the stratified log-rank test and the stratified Cox model.

In case the proportional hazards assumption does not hold, Restricted Mean Survival Time (RMST) method may be conducted for OS to account for the possible nonproportional hazards effect as a sensitivity analysis.

#### **8.6.1.2 Progression-free Survival**

The nonparametric Kaplan-Meier method will be used to estimate the PFS curve in each treatment group. The treatment difference in PFS will be assessed by the stratified log-rank test. A stratified Cox proportional hazard model with Efron's method of tie handling will be used to assess the magnitude of the treatment difference (i.e., hazard ratio) between the treatment groups. The hazard ratio and its 95% CI from the stratified Cox model with Efron's method of tie handling and with a single covariate for treatment will be reported. The stratification factors used for randomization (see Section 5.4 – Stratification) will be applied to both the stratified log-rank test and the stratified Cox model.

Since disease progression is assessed periodically, PD can occur any time in the time interval between the last assessment where PD was not documented and the assessment when PD is documented. For the primary analysis, for the subjects who have PD, the true date of disease

progression will be approximated by the date of the first assessment at which PD is objectively documented per RECIST 1.1 by BICR, regardless of discontinuation of study drug. Death is considered as a confirmed PD event.

In order to evaluate the robustness of the PFS endpoint per RECIST 1.1 by BICR, 2 sensitivity analyses with a different set of censoring rules will be performed. The first sensitivity analysis is the same as the primary analysis except that the data for any subject who misses more than 1 disease assessment (with or without a subsequent death or progression) are censored at the last disease assessment prior to missing visits. The second sensitivity analysis is the same as the primary analysis except that it considers discontinuation of treatment or initiation of an anticancer treatment subsequent to discontinuation of study-specified treatments, whichever occurs later, to be a PD event for subjects without documented PD or death. If a subject meets multiple criteria for censoring, the censoring criterion that occurs earliest will be applied. The censoring rules for primary and sensitivity analyses are summarized in [Table 11](#). In case there is an imbalance between the treatment groups on disease assessment schedules or censoring patterns, we will perform an additional PFS sensitivity analysis using time from randomization to scheduled tumor assessment time as opposed to actual tumor assessment.

In case the proportional hazards assumption is not valid, RMST method may be conducted for PFS to account for the possible nonproportional hazards effect as a sensitivity analysis.

Table 11 Censoring Rules for Primary and Sensitivity Analyses of PFS

Situation	Primary Analysis	Sensitivity Analysis 1	Sensitivity Analysis 2
PD or death documented after $\leq 1$ missed disease assessment, and before new anticancer therapy, if any	Progressed at date of documented PD or death	Progressed at date of documented PD or death	Progressed at date of documented PD or death.
Death or progression immediately after $\geq 2$ consecutive missed disease assessments, or after new anticancer therapy	Censored at last disease assessment prior to the earlier date of $\geq 2$ consecutive missed disease assessment and new anticancer therapy, if any	Progressed at date of documented PD or death	Progressed at date of documented PD or death.
No PD and no death; and new anticancer treatment is not initiated	Censored at last disease assessment	Censored at last disease assessment	Progressed at treatment discontinuation due to reasons other than CR; otherwise censored at last disease assessment if still on study treatment or completed study treatment.

Situation	Primary Analysis	Sensitivity Analysis 1	Sensitivity Analysis 2
No PD and no death; new anticancer treatment is initiated	Censored at last disease assessment before new anticancer treatment	Censored at last disease assessment	Progressed at date of new anticancer treatment.

Abbreviations: PFS=progression-free survival; PD=progressive disease.

### 8.6.1.3 Objective Response Rate

The stratified Miettinen and Nurminen method will be used for comparison of the ORR between the 2 treatment groups. The difference in ORR and its 95% CI from the stratified Miettinen and Nurminen method with strata weighting by sample size will be reported. The stratification factors used for randomization (see Section 5.4– Stratification) will be applied to the analysis. Subjects without assessments are considered nonresponders.

### 8.6.1.4 Duration of Response

For subjects who demonstrate CR or PR, DOR is defined as the time from first documented evidence of CR or PR until disease progression or death due to any cause, whichever occurs first. Censoring rules for DOR are summarized in [Table 12](#).

For DOR analysis, a summary of the reasons responding subjects are censored will also be provided. Responding subjects who are alive, have not progressed, have not initiated new anticancer treatment, have not been determined to be lost to follow-up, and have had a disease assessment within ~ 5 months of the data cutoff date are considered ongoing responders at the time of analysis. If a subject meets multiple criteria for censoring, the censoring criterion that occurs earliest will be applied.

Table 12 Censoring Rules for Duration of Response

Situation	Date of Progression or Censoring	Outcome
No progression nor death, no new anticancer therapy initiated	Last adequate disease assessment	Censor (nonevent)
No progression nor death, new anticancer therapy initiated	Last adequate disease assessment before new anticancer therapy initiated	Censor (nonevent)
Death or progression immediately after $\geq 2$ consecutive missed disease assessments or after new anticancer therapy, if any	Earlier date of last adequate disease assessment prior to $\geq 2$ missed adequate disease assessments and new anticancer therapy, if any	Censor (nonevent)
Death or progression after $\leq 1$ missed disease assessments and before new anticancer therapy, if any	PD or death	End of response (Event)
Abbreviations: PD = progressive disease A missed disease assessment includes any assessment that is not obtained or is considered inadequate for evaluation of response.		

If sample size permits, DOR will be summarized descriptively using the Kaplan-Meier method. Only the subset of subjects who show a CR or PR will be included in this analysis.

#### **8.6.1.5 Change from Baseline in Global Health Status/Quality of Life**

The time point for the mean change from baseline will be determined based on blinded data review prior to the database lock for any PRO analysis and documented in the sSAP.

To assess the treatment effects on the PRO score change from baseline in the global health status/quality of life, a constrained longitudinal data analysis (cLDA) model proposed by Liang and Zeger [43] will be applied, with the PRO score as the response variable, and treatment, time, the treatment by time interaction, and stratification factors used for randomization (see Section 5.4 – Stratification) as covariates. The treatment difference in terms of least square (LS) mean change from baseline will be estimated from this model together with 95% CI. Model-based LS mean with 95% CI will be provided by treatment group for PRO scores at baseline and post-baseline time point.

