#### **8.6.1.7 Analysis Strategies for Key Efficacy Endpoints**

Table 13 summarizes the primary analysis approach for primary and secondary efficacy endpoints. Sensitivity analysis methods are described above for each endpoint as applicable.

The strategy to address multiplicity issues with regard to multiple efficacy endpoints, and interim analyses is described in Section 8.7 – Interim Analyses and in Section 8.8 – Multiplicity.

Table 13 Analysis Strategy for Key Efficacy Endpoints

Endpoint/Variable	Statistical Method a	Analysis Population	Missing Data Approach
Primary:			
OS	Test: Stratified log-rank test to assess the treatment difference Estimation: Stratified Cox model with Efron’s tie handling method to assess the magnitude of treatment difference	ITT	
 
Censored at last known alive date.
 

PFS per RECIST 1.1 by BICR	Test: Stratified log-rank test to assess the treatment difference Estimation: Stratified Cox model with Efron’s tie handling method to assess the magnitude of treatment difference	ITT	
 
Primary censoring rule
 
Sensitivity analysis 1
 
Sensitivity analysis 2
 
 (More details are in Table 11 ).
Secondary :			
ORR per RECIST 1.1 by BICR	Stratified Miettinen and Nurminen method with sample size weights	ITT	Subjects without assessments are considered nonresponders.
DOR per RECIST 1.1 by BICR	Summary statistics using Kaplan-Meier method	All responders in ITT	Censoring rules in Table 12 .
Change from baseline in global health status/quality of life (items 29 and 30)	cLDA model	PRO FAS	Missing at random
TTD	Test: Stratified log-rank test to assess the treatment difference Estimation: Stratified Cox model with Efron’s tie handling method to assess the magnitude of treatment difference	PRO FAS	Censoring at the last available assessment.

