#### **8.9 Sample Size and Power Calculations**

The study plans to randomize approximately 568 subjects with 1:1 ratio into the pembrolizumab plus ipilimumab arm and the pembrolizumab plus placebo arm.

With 389 PFS events, the study has ~ 87% power for detecting a hazard ratio of 0.69 at 0.60% (one-sided) significance level. With 361 deaths, the study has ~ 90% power for detecting a hazard ratio of 0.7 at 1.90% (one-sided) significance level.

The above sample size and power calculations for PFS and OS assume the following, with control arm assumption estimated from the pembrolizumab arm from KEYNOTE-042 in the PD-L1 TPS  $\geq 50\%$  population:

- PFS follows a piecewise exponential distribution with a median of 6.5 months before 6.5 months and a median of 14.5 months after 6.5 months in the control group.
- OS follows an exponential distribution with a median of 20 months for the control group.
- The HR for PFS and OS between the experimental and control groups is 0.69 and 0.7, respectively.
- Enrollment period of 20 months.
- A yearly dropout rate of 13% and 1% for PFS and OS, respectively.

The sample size and power calculations were performed in the software EAST and R (package “gsDesign”).

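### Does listing a treatment effect among the model terms undo the equal-baseline constraint in the quality-of-life analysis?

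*Combined protocol and SAP*

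**What the plan says.** Section 8.6.1.5 analyses the EORTC QLQ-C30 global health score with "a constrained longitudinal data analysis (cLDA) model", cites a source for the method, and describes the fit "with the PRO score as the response variable, and treatment, time, the treatment by time interaction, and stratification factors used for randomization". The reported effect is a between-arm contrast: "The treatment difference in terms of least square (LS) mean change from baseline will be estimated from this model together with 95% CI". The section then adds: "Model-based LS mean with 95% CI will be provided by treatment group for PRO scores at baseline and post-baseline time point".

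Table 13 in Section 8.6.1.7 again gives the cLDA model as the method for this endpoint. The population is the PRO full analysis set and the missing-data entry is "Missing at random". Section 8.5.3 sets that population as those "defined as subjects who have at least 1 PRO assessment available and have received at least 1 dose of study medication" (quoted from its definition).

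No section says that the two arms share one baseline mean, and none says that they have separate ones. Section 8.0 places the PRO analysis plan in the supplemental SAP, which is not among the documents. Section 8.6.1.5 also sends the choice of time point there.

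**The concern.** In a cLDA the baseline score is one of the repeated responses, and randomisation justifies a single baseline mean for both arms. Treatment then enters only at post-baseline times. Section 8.6.1.5 puts the score itself in the response and reports model-based means at baseline, so baseline is a level of time. A treatment main effect plus the full treatment-by-time interaction is then a saturated arm-by-time mean model, in which each arm has its own baseline mean. The promise of baseline means by arm seems to confirm this.

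If the model were coded that way, the complete-data estimate would be the raw difference in mean change. The confidence interval would be wider than the named method gives, and a chance baseline difference between arms would pass into the estimate uncorrected. The reader would be told that a cLDA had been used when it had not.

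**Working it through.** **No stated figure to reproduce.** The documents give no standard deviation, correlation, standard error or power for this endpoint. The only input taken from them is the sample size: "The study plans to randomize approximately 568 subjects with 1:1 ratio" (Section 8.9), so n = 568/2 = 284 per arm. The correlation rho is assumed, and results are in units of a common standard deviation.

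**Counting parameters.** With T time points including baseline, treatment + time + treatment-by-time without restriction has 2T means. The constrained model has 2T − 1, because the baseline treatment difference is fixed at zero. For T = 2 that is 4 against 3. Imposing one restriction on the listed effects turns the first model into the second, so the list is compatible with either.

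**Size of the difference if the restriction were left out.** Take complete data, one post-baseline visit and equal variances. Let D0 and D1 be the between-arm differences at baseline and follow-up.

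- Unconstrained estimate: D1 − D0, variance 4·SD²·(1 − rho)/n.
- Constrained estimate: D1 − rho·D0, variance 2·SD²·(1 − rho²)/n.
- Ratio of standard errors: sqrt(2/(1 + rho)).

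At rho = 0.5: sqrt(4 × 0.5/284) = 0.0839 and sqrt(2 × 0.75/284) = 0.0727, a ratio of 1.155.

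| rho (assumed) | SE unconstrained | SE constrained | SE ratio | Variance ratio |
|---|---|---|---|---|
| 0.3 | 0.0993 | 0.0801 | 1.24 | 1.54 |
| 0.5 | 0.0839 | 0.0727 | 1.155 | 1.33 |
| 0.7 | 0.0650 | 0.0599 | 1.085 | 1.18 |

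Over rho from 0.2 to 0.8 the ratio runs from 1.29 down to 1.05. With five time points including baseline, compound symmetry and 10% dropout per visit (all assumed), it runs from 1.20 to 1.04 at the last visit.

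**Chance imbalance.** The two estimates differ by −(1 − rho)·D0. Under randomisation D0 has mean zero and standard error sqrt(2/284) = 0.084 SD, so at rho = 0.5 a typical shift is 0.5 × 0.084 = 0.042 SD. This is the same loss seen from another side: (1 − rho)²·2/n = 0.25 × 2/284 = 0.0018, which equals the gap between the two variances at rho = 0.5 (0.0070 − 0.0053, up to rounding). Since D0 averages zero, both estimates are unbiased in expectation, and the unconstrained interval, though wider, is valid.

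**Which model the text specifies.** Two places name the constrained model, and one of them cites its source. The list names effects and does not say how they are parameterised. The baseline means by arm do not decide the matter: under the constraint they are still reported, and they coincide apart from any covariate averaging. The reading that agrees with every sentence is the constrained one.

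**The case for a change.** The best case for a change is that programmers code effect lists, not method names. Someone who enters treatment, time and their interaction, with baseline as a time level, gets the unconstrained model unless they add a restriction that Section 8.6.1.5 never mentions. Two analysts could then reach different intervals from the same text. At rho = 0.5 the variance is 33% larger, which is like losing a quarter of the PRO sample (1 − 1/1.33 = 0.25). The supplemental SAP cannot be credited with a fix that no one here has seen. The trial is now unblinded, PRO data collected before Amendment 06 exist, and Section 10.7 intends publication even after early termination. One sentence would settle it.

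Part of this stands. The equal-baseline condition is not written out, and the precision loss is real if it is ignored. But equal baseline means are what distinguish this model from an ordinary longitudinal one, so fitting without them departs from the plan. The added sentence would only restate the method already chosen. The percentages hold only for a miscoded fit and an assumed correlation. Little rests on the interval: objective 3 in Section 3.2 carries no hypothesis, the alpha scheme in Section 8.8 covers only PFS, OS and ORR, and Section 8.6.1 treats p-values outside that scheme as nominal.

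**Conclusion.** No change is needed. This is a gap in detail that a competent analyst fills correctly by applying the method the SAP names. With the constraint imposed, the standard error is not inflated at all.

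Without it, the standard error would be about 8% to 24% larger for an assumed correlation of 0.7 to 0.3 (complete data, one post-baseline visit, equal variances). With five time points and assumed dropout the figure is 4% to 20% over correlations of 0.8 to 0.2. That would be lost precision on a secondary endpoint outside the alpha scheme, with no bias in expectation and no type I error inflation.

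The practical stake is smaller still. Sections 4.2.3.2 and 7.1.2.8 record that PRO collection has stopped, and the note opening Section 8.0 rules out further prespecified analysis of secondary endpoints. The point could matter only if PRO data gathered before Amendment 06 are reported, and there the named method already gives the right model. Whether the supplemental SAP writes the constraint out cannot be checked from these documents. The conclusion does not depend on it.
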